6.1.4 Device Calibration

No calibration of the device is required. Each device is single use and disposable after use.

6.1.5 Storage Condition

The device will be stored at room temperature within our embryology laboratory as per manufacturer protocol. Receipt of the device, including number of devices received, lot number(s) of the devices, open and close dates for each lot, and certificates of analysis for each lot will be recorded and/or filed. Unused devices at the conclusion of the study will be returned to the study sponsor.

6.1.6 Concomitant therapy

None

6.1.7 Restrictions

Restrictions for use of the device will include severe male factor defined as an initial ejaculate sample with <0.5 million total motile sperm and/or no sperm observed with progressive forward motility (forward progression grade of 2.) Any surgically derived sperm will be excluded from the study. Additionally, when orders are written for ICSI per embryologist, any specimen not meeting above criteria for ICSI (see section 6.1.2), will be inseminated via IVF and therefore, their oocytes will not be inseminated with ZyMot separated sperm.

6.2 Assessments

6.2.1 Efficacy

The efficacy of the device will be evaluated by our primary objective, percentage of good quality embryos available following ICSI insemination with ZyMot separated sperm compared to insemination with density gradient separated sperm.

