The study will be completed once 408 oocytes are randomized, which is anticipated to be in approximately 1-2 years.

Study Design

Subjects meeting inclusion criteria will be approached for inclusion into the study and informed consent will be obtained from the patient and the sperm source. Controlled ovarian hyperstimulation will be performed followed by oocyte retrieval as per our standard protocol. On the day of oocyte retrieval, sperm samples will be split into two samples and processed via density gradient (our standard sperm separation technique) and ZyMot (our experimental arm). Sperm parameters will be evaluated pre and post-sperm separation following ZyMot and density gradient. Following oocyte retrieval, the oocytes will be assessed as per our standard fashion. In the event that the oocytes will be inseminated via intracytoplasmic sperm injection (ICSI) and there are 6 or more mature oocytes, half of the oocytes will be inseminated via ZyMot processed sperm and half with sperm processed via density gradient. In the event that there are less than 6 mature oocytes or the insemination technique will be IVF, the oocytes will only be inseminated with sperm processed via density gradient. Additionally, in the event that the sperm sample is insufficient for ZyMot processing (<0.5 million total motile sperm and/or no sperm observed with progressive forward motility), the sperm will not be processed with ZyMot and the patient will be withdrawn from the study.

The primary outcome will be percentage of good quality embryo formation resulting from oocytes inseminated following ZyMot separated sperm compared to density gradient separated sperm. Secondary outcomes will include percentage of euploid embryos in the

event that PGT-A is performed, pregnancy rates, miscarriage rates, live birth rates, and sperm parameters following sperm processing. Decision to transfer an embryo will be made as per our standard protocols regardless of the sperm processing technique.

Study Population

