- Following oocyte retrieval, oocytes will be denuded of their cumulus cells per standard protocol. If at least 6 mature oocytes (determined by visualization of a polar body) are present, half the oocytes will be ICSI inseminated with sperm prepared via ZyMot device and half will be ICSI inseminated with sperm prepared with density gradient. Patients whose patient identification number (PID) is even will have the group of oocytes inseminated with sperm separated via ZyMot device recorded first in the eMR gamete sheet (beginning with oocyte #1.) Patients with an odd PID will have the oocytes inseminated with sperm separated via density gradient recorded first in the eMR gamete sheet (beginning with oocyte #1.) In the event of an odd number of oocytes, the patients with even PIDs will have the extra oocyte inseminated with sperm separated via Zymot device and patients with odd PIDs will have the extra oocyte inseminated with sperm separated via density gradient. Inseminated oocytes will be grouped into separate wells of a LifeGlobal 4 well GPS dish (Cooper Surgical) by the sperm separation method — one well will contain all oocytes inseminated with sperm selected by ZyMot device and a separate well will contain all oocytes inseminated with sperm selected by density gradient centrifugation.

Control Group of Oocytes:

Half of the eggs will be inseminated via ICSI using sperm selected by conventional gradient centrifugation.

Treatment Group of Oocytes:

- Half of the eggs will be inseminated via ICSI using sperm selected using ZyMot.
- Fertilization assessment will be performed between 16 and 18 hours after insemination and normal fertilization will be considered visualization of exactly two pronuclei. Normally fertilized oocytes (embryos) will then be cultured in Continuous Single Culture Medium — NX Complete (Irvine Scientific) in separate, numbered droplets in LifeGlobal microdrop GPS dishes (Cooper Surgical.) The numbers of the droplets will correlate to oocyte/embryo number in the eMR gamete sheet and, thereby, also correlate to the type of sperm used for the insemination. Development of the embryos will be assessed on culture days 5 and 6 and embryo stage and grade will be recorded for each embryo.

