6.4.2 Sample Size Considerations

For a two-tailed McNemar's test with alpha level 0.05, the following relation yields an approximate power of 80% to detect a difference d between proportions p_1 and p_2 : $n = \frac{16pq(1-r)}{d^2}$ where n is the size of the sample (i.e. number of eggs), $p = (p_1 + p_2)/2$, $q = 1 - p$, $d = |p_2 - p_1|$, and r is the phi

correlation coefficient¹. We will assume a conservative estimate for the correlation $r=0.5$. Assuming a 48% good quality blastocyst development rate and a 7% improvement in good quality blastocyst development with ZyMoT, we would need a total of 408 oocytes randomized to either density gradient or ZyMoT separation, which would equate to 68 patient/sperm source dyads each with ≥ 6 eggs retrieved.

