6.4.5 Handling of Missing Data

¹ Lehr, R. G. 2001. Some practical considerations and a crude formula for estimating sample size for McNemar's test. Drug Information Journal, 35: 1227-1233.

Missing data will be maintained as missing in the analysis datasets, unless specified otherwise. If it is deemed that imputing data is necessary, the analysis dataset will contain a new variable with the imputed value and the original variable value will be maintained as missing.

7 - Trial Administration

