7.12 Data Safety Monitoring Plan

Halfway through recruitment of sample size, preliminary results will be analyzed by the principal investigator and co-investigators. If the primary endpoint is adversely affected by study arm, the study will be terminated. The primary endpoint will be percentage of good quality embryos comparing those inseminated with density processed sperm and ZyMot processed sperm. In the event that there is a statistically significant ($p < 0.05$) percentage of higher quality embryo formation in the embryos created via sperm inseminated with density processed sperm compared to ZyMot processed sperm, the study will be terminated. Preliminary analysis of the results will be communicated promptly to the IRB.

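### The denominator of the primary percentage is not fixed: the wording varies between inseminated oocytes and embryos, and no rule says how an unfertilised oocyte is scored.

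*Combined protocol and SAP*

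**What the plan says.** Two places point to inseminated oocytes as the denominator. The Study Design part of the synopsis gives the primary outcome as "percentage of good quality embryo formation resulting from oocytes inseminated following ZyMot separated sperm". Section 6.4.2 presents its sample-size relation with the clause "where n is the size of the sample (i.e. number of eggs" and arrives at 408 oocytes.

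Two places can be read as per embryo. Section 6.2.1 measures efficacy by the "percentage of good quality embryos available following ICSI insemination with ZyMot separated sperm". Section 7.12, which holds the interim stopping rule, says: "The primary endpoint will be percentage of good quality embryos comparing those inseminated with density processed sperm and ZyMot processed sperm".

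Section 6.1.2 bears on what an embryo is. After the fertilisation check, "Normally fertilized oocytes (embryos) will then be cultured", and stage and grade are then recorded for each embryo on days 5 and 6.

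Three sections that could settle the matter do not:
- Section 5.2.1 defines a good-quality embryo (a day 5 or 6 blastocyst graded good or fair). That is the numerator only.
- Section 6.4.3.1 names McNemar's test but does not say how an oocyte that never receives a grade enters it.
- Section 6.4.5 says "Missing data will be maintained as missing in the analysis datasets", unless specified otherwise, and allows imputation. It does not mention unfertilised oocytes.

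**The concern.** Oocytes are allocated to a sperm preparation before fertilisation. Normal fertilisation is then observed, is listed as a secondary outcome in 5.2.2, and may itself be changed by the preparation. Dividing by all inseminated oocytes keeps the two groups as they were allocated. Dividing by normally fertilised oocytes compares two groups selected after allocation, and the selection may differ between arms.

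The two percentages can give different answers. A preparation that fertilises fewer oocytes but yields as many good blastocysts looks better per embryo. One that fertilises more oocytes and yields more good blastocysts in proportion looks no different per embryo. With the denominator open, the choice could be made after the data are seen. It also reaches the interim look, because 6.4.3.5, 7.12 and 7.14 stop the study on the same undefined percentage.

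**Working it through.** **Inputs from the plan (6.4.2).** Two-sided McNemar's test, alpha 0.05, approximate power 80%, r = 0.5, and 48% v 55% (reading the 7% improvement as 7 percentage points). The documents give no fertilisation rate, so every rate below is an assumption.

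**1. The plan's own figure.** With p = (0.48 + 0.55)/2 = 0.515, q = 0.485 and d = 0.07:

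n = 16pq(1 − r)/d² = 16 × 0.515 × 0.485 × 0.5 / 0.0049 = 407.8, so 408.

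The stated figure reproduces.

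**2. How the two percentages are related.** Let f be the normal fertilisation rate and b the proportion of normally fertilised oocytes that become good-quality blastocysts. The per-embryo rate is b. The per-inseminated-oocyte rate is f × b.

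**3. Illustrations in both directions (f assumed).**

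| Case | Quantity | Density gradient | ZyMot |
|---|---|---|---|
| A: equal yield, ZyMot fertilises fewer | f | 75% | 65.5% |
| | Per inseminated oocyte | 36% | 36% |
| | Per embryo | 0.36/0.75 = 48.0% | 0.36/0.655 = 55.0% |
| B: equal b, ZyMot fertilises more | f | 70% | 80.2% |
| | Per embryo | 68.6% | 68.6% |
| | Per inseminated oocyte | 0.70 × 0.686 = 48.0% | 0.802 × 0.686 = 55.0% |

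In A, the per-embryo analysis shows the full 7-point target with no gain in blastocysts per oocyte. In B, it hides a 7-point gain per oocyte. The fertilisation gaps required are 9.5 points (A) and 10.2 points (B).

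**4. What this does to the power.** Section 6.4.2 does not say what the 48% is a percentage of.

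- *If it is per inseminated oocyte and analysed that way*, the inputs stand and 408 is unchanged by this issue.
- *If it is per embryo but the analysis is per inseminated oocyte*, both rates are multiplied by f. Taking f equal in both arms, keeping r = 0.5 and counting n in oocytes as the plan does, power = Φ(√[n d² / (2pq(1 − r))] − 1.96). For 48% v 55% at n = 408 this gives 80.8%, in line with the plan.

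| f (assumed, both arms) | Rates per inseminated oocyte | Difference | Power at 408 | n by the plan's relation |
|---|---|---|---|---|
| 65% | 31.2% v 35.75% | 4.55 points | 49.5% | 861 |
| 80% | 38.4% v 44.0% | 5.6 points | 63.2% | 618 |

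**The case against.** The best reply is that the plan means inseminated oocytes and is only loosely worded. Much of the text supports this. Most statements of the endpoint speak of embryo formation, and the synopsis ties it to inseminated oocytes. Section 5.3.1 links the 408 oocytes to the primary outcome, sister oocytes are the randomised unit, and 6.4.3.2 adjusts for the size of the egg cohort. Section 7.12 speaks of what is inseminated, and only oocytes are. Section 6.3.1 applies the word embryos to oocytes still awaiting their fertilisation check, so the parenthesis in 6.1.2 cannot fix the meaning elsewhere. All this stands. A reader might infer that the plan states two conflicting denominators; it does not, because no passage states a per-embryo denominator outright.

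A reader might also infer that 6.4.5 drops unfertilised oocytes. It does not say so. An oocyte that fails to fertilise cannot become a day 5 or 6 blastocyst, so its outcome can be regarded as a known failure. It would be left out only if its absent grade were coded as missing. The plan neither requires nor rules out that coding.

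On size, the fertilisation rates are invented for illustration. Case A also runs against the plan's rationale: 2.1 cites data linking DNA fragmentation to lower fertilisation and reports less fragmentation with ZyMot. Case B follows that rationale, and there the per-embryo analysis would hide a benefit.

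The power figures carry a further caveat. The relation is for a matched-pair test, yet the plan enters single oocytes as n. Read as pairs, 408 oocytes make at most 204 pairs, and the same formula gives about 52% power before any fertilisation loss. That is a separate ambiguity, and the figures above do not isolate the denominator from it.

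**Conclusion.** The point holds as an undefined denominator with inconsistent wording, together with a missing scoring rule for oocytes that do not fertilise. It matters because a literal per-embryo reading of 6.2.1 and 7.12 conditions both the primary comparison and the interim stopping decision on a post-allocation outcome. Under assumed fertilisation gaps of about 10 points, the choice of denominator alone can create or hide the whole 7-point target.

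It would be tempting to conclude that 408 is wrong or that the trial is underpowered for this reason. The documents do not support that: 408 reproduces, and it is unaffected if the 48% is per inseminated oocyte. The 50–63% power range applies only if the 48% is per embryo, the analysis is per inseminated oocyte, fertilisation is 65–80% and equal in both arms, r stays at 0.5, and n is counted in oocytes.

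**What to change.** - In 5.2.1, 6.2.1, 6.4.3.1 and 7.12, define the primary endpoint in the same words: good-quality day 5 or 6 blastocysts divided by all mature oocytes inseminated in that arm. This matches the unit of n in 6.4.2.
- Count oocytes that are unfertilised, abnormally fertilised, degenerated, arrested or ungraded as not good quality, and state that they are not missing data under 6.4.5.
- Report the rate per normally fertilised oocyte as a supportive result.
- State in 6.4.2 which denominator the 48% uses. If it is per embryo, restate the power.

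The cost is protocol and SAP wording. The gamete sheet described in 6.1.2 already links each oocyte number to the sperm preparation, so no new data are needed. The downside is that the observed rate, and possibly the stated power, may look less favourable.

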6.2.2 Safety/Pregnancy-related policy

Not Applicable.

6.2.2.1 Adverse Events Definition and Reporting

Definitions

Unanticipated Problems Involving Risk to Subjects or Others Any incident, experience, or outcome that meets all of the following criteria: Unexpected in nature, severity, or frequency (i.e. not described in study-related documents such as the IRB-approved protocol or consent form, the investigators brochure, etc.)

Related or possibly related to participation in the research (i.e. possibly related means there is a reasonable possibility that the incident experience, or outcome may have been caused by the procedures involved in the research)

Suggests that the research places subjects or others at greater risk of harm (including physical, psychological, economic, or social harm).

Adverse Event

An **adverse event** (AE) is any symptom, sign, illness or experience that develops or worsens in severity during the course of the study. Intercurrent illnesses or injuries should be regarded as adverse events. Abnormal results of diagnostic procedures are considered adverse events if the abnormality:

- results in study withdrawal
- is associated with a serious adverse event
- is associated with clinical signs or symptoms
- leads to additional treatment or to further diagnostic tests
- is considered by the investigator to be of clinical significance

Serious Adverse Event

Adverse events are classified as serious or non-serious. A serious adverse event is any AE that is:

- fatal
- life-threatening
- requires or prolongs hospital stay
- results in persistent or significant disability or incapacity
- a congenital anomaly or birth defect
- an important medical event
- Important medical events are those that may not be immediately life threatening, but are clearly of major clinical significance. They may jeopardize the subject, and may require intervention to prevent one of the other serious outcomes noted above. For example, drug overdose or abuse, a seizure that did not result in in-patient hospitalization or intensive treatment of bronchospasm in an emergency department would typically be considered serious.

All adverse events that do not meet any of the criteria for serious should be regarded as **non-serious adverse events**.

Preexisting Condition

A preexisting condition is one that is present at the start of the study. A preexisting condition should be recorded as an adverse event if the frequency, intensity, or the character of the condition worsens during the study period.

General Physical Examination Findings

At screening, any clinically significant abnormality should be recorded as a preexisting condition. At the end of the study, any new clinically significant findings/abnormalities that meet the definition of an adverse event must also be recorded and documented as an adverse event.

Post-study Adverse Event

All unresolved adverse events should be followed by the investigator until the events are resolved, the subject is lost to follow-up, or the adverse event is otherwise explained. At the last scheduled visit, the investigator should instruct each subject to report any subsequent event(s) that the subject, or the subject's personal physician, believes might reasonably be related to participation in this study. The investigator should notify the study sponsor of any death or adverse event occurring at any time after a subject has discontinued or terminated study participation that may reasonably be related to this study. The sponsor should also be notified if the investigator should become aware of the development of cancer or of a congenital anomaly in a subsequently conceived offspring of a subject that has participated in this study.

Recording of Adverse Events

At each contact with the subject, the investigator must seek information on adverse events by specific questioning and, as appropriate, by examination. Information on all adverse events should be recorded immediately in the source document, and also in the appropriate adverse event module of

the case report form. All clearly related signs, symptoms, and abnormal diagnostic procedures results should be recorded in the source document, though should be grouped under one diagnosis.

All adverse events occurring during the study period must be recorded. The clinical course of each event should be followed until resolution, stabilization, or until it has been determined that the study treatment or participation is not the cause. Serious adverse events that are still ongoing at the end of the study period must be followed up to determine the final outcome. Any serious adverse event that occurs after the study period and is considered to be possibly related to study participation should be recorded and reported immediately.

Reporting of Serious Adverse Events and Unanticipated Problems

For Narrative Reports of Safety Events

If the report is supplied as a narrative, the minimum necessary information to be provided at the time of the initial report includes:


• Study identifier• Study Center• Subject number• A description of the event• Date of onset	
• Current status• Whether study treatment was discontinued• The reason why the event is classified as serious• Investigator assessment of the association between the event and study treatment
---	--

Investigator reporting: notifying the IRB Federal regulations require timely reporting by investigators to their local IRB of unanticipated problems posing risks to subjects or others. The following describes the NYULMC IRB reporting requirements, though Investigators at participating sites are responsible for meeting the specific requirements of their IRB of record.

Report promptly, but no later than 5 working days:

Researchers are required to submit reports of the following problems promptly but no later than 5 working days from the time the investigator becomes aware of the event:

Unanticipated problems including adverse events that are unexpected and related

Unexpected: An event is "unexpected" when its specificity and severity are not accurately reflected in the protocol-related documents, such as the IRB-approved research protocol, any applicable investigator brochure, and the current IRB-approved informed consent document and other relevant sources of information, such as product labeling and package inserts.

Related to the research procedures: An event is related to the research procedures if in the opinion of the principal investigator or sponsor, the event was more likely than not to be caused by the research procedures.

Harmful: either caused harm to subjects or others, or placed them at increased risk

Other Reportable events: The following events also require prompt reporting to the IRB, though no later than 5 working days:

Complaint of a research subject when the complaint indicates unexpected risks or the complaint cannot be resolved by the research team.

Protocol deviations or violations (includes intentional and accidental/unintentional deviations from the IRB approved protocol) for any of the following situations:

one or more participants were placed at increased risk of harm

the event has the potential to occur again

the deviation was necessary to protect a subject from immediate harm

Breach of confidentiality

New Information indicating a change to the risks or potential benefits of the research, in terms of severity or frequency. (e.g. analysis indicates lower-than-expected response rate or a more severe or frequent side effect; FDA labeling change or withdrawal from market)

Reporting Process

The reportable events noted above will be reported to the IRB using a Reportable New Information submission and will include a description of the event with information regarding its fulfillment of the above criteria, follow-up/resolution, and need for revision to consent form and/or other study documentation. Copies of each report and documentation of IRB notification and receipt will be kept in the Clinical Investigator's study file.

